11. STATISTICAL ANALYSIS

The baseline corrected AUC for carotenoids will be calculated by the trapezoidal approach, using the PK functions plug-in for Microsoft Excel. Negative values, if occurring, will be included as such.

Mean AUC between the test meals will be compared by a repeated measures ANOVA design (i.e. each subject will be compared against himself at 3 time points), followed by post-hoc test comparisons (Fisher protected LSD test) given a significant Fisher-F test. No log-transformation will be carried out, but AUC values will be baseline corrected. Thus, a model with the observed dependent factor baseline-corrected-AUC for each carotenoid (lycopene, beta-carotene) and the triglycerides will be run, with subject, randomization sequence, test meal as fixed factor and baseline carotenoid concentration as a covariate.

Normal distribution will be verified by Q-Q-plots and Kolmogorov-Smirnoff tests.

Non parametrical analysis (Friedman tests followed by individual t-tests) may be chosen in case data is not normally distributed, though based on earlier studies data normally follows normal distribution. Log-transformation will not be carried out.

P-values below 0.05 will be interpreted as statistically significant (2-tailed). Data analysis will be performed with SPSS 19.0 for Windows (SPSS Inc., Chicago IL).

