2.4 Trial design

This is a post-prandial double blinded, randomized and controlled cross-over study with 3 periods and six sequences.

A 6x3 Williams Crossover design is applied for the six sequences. Equal allocation of six patients per sequence is planned. Patients meeting the inclusion criteria will receive three different interventions (2 different meals with added protein sources and one control meal where no protein is added) at three different time points following a one-week washout period.

A	B	C
B	C	A
C	A	B

C	B	A
A	C	B
B	A	C

Figure 1: 6x3 Williams Crossover Design

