2.6 Sample Size

It is assumed that two different outcomes will be tested as dependent variables and all pairwise comparisons will be performed. First lycopene and then beta-carotene will be tested. This will lead to three statistical tests per carotenoid readout: with the original alpha risk of 0.05 the corrected alpha risk would then be $0.05/6=0.083$ i.e. 0.83%. The Bonferroni adjustment will be used to keep the family-wise error at the specified error level and thus with the total number of pairwise comparisons equal to 6 each pairwise test is at the two-sided 0.83% significance level.

Area under the time – carotenoid concentration is assumed as main outcome for the sample size calculation.

When there are 2 outcomes (lycopene and beta-carotene), 3 treatments and a sample size of 4 in each of the 6 sequences, a 6x3 Williams Crossover inequality test of paired differences will have 96% power to detect a minimum difference of 4% of the area under time curve (AUC) (difference between 20% and 24% of AUC) or greater, assuming that the standard deviation of the paired differences is 4% at the 0.83% significance level. This leads to a total sample size of N=24 participants.

In case of one drop-out per sequence (n=3 per sequence), the power will reduce to 83%, which will still provide sufficient statistical strength. Sample size calculation was performed in nQuery 8 (version 8.3.1.0).

[figure not shown]

Figure 3 Power (%) vs. Sample Size per Sequence; minimum difference = 4%, SD = 4%, significance level = 0.8%

Figure 4 Power (%) vs. Minimum Expected Difference; n per sequence = 4, $SD = 4\%$, significance level = 0.8%

[figure not shown]

Figure 5 Power (%) vs. Standard deviation; $n=4$ per sequence, mean difference = 4%, significance level = 0.8%

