2.7 Framework

A superiority hypothesis testing framework is assumed. For the main outcomes, the following comparisons are planned:

a) Difference in AUC (concentration over time) of circulating carotenoid (lycopene) in the plasma TRL fraction:

1. Protein containing meal 1 vs. control meal
2. Protein containing meal 2 vs. control meal
3. Protein containing meal 1 vs. protein containing meal 2

b) Difference in AUC (concentration over time) of circulating carotenoid (beta-carotene) in the plasma TRL fraction:

4. Protein containing meal 1 vs. control meal
5. Protein containing meal 2 vs. control meal
6. Protein containing meal 1 vs. protein containing meal 2

As a secondary outcome:

c) Difference in AUC (concentration over time) of triglycerides in the plasma:

1. Protein containing meal 1 vs. control meal
2. Protein containing meal 2 vs. control meal
3. Protein containing meal 1 vs. protein containing meal 2
- 4.

d) Difference in AUC (concentration over time) of total carotenoids in the plasma:

5. Protein containing meal 1 vs. control meal
6. Protein containing meal 2 vs. control meal
7. Protein containing meal 1 vs. protein containing meal 2

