3.1 P- values and multiplicity adjustment

As two statistical tests will be performed per main outcome (beta-carotene and lycopene), the total number of comparisons will be 6 (3 x 2) and therefore multiplicity correction will be applied. A Bonferroni corrected p-value will be used at that level: $\frac{\alpha}{2} = \frac{0.05}{2} = 0.025$. For the three post-hoc tests within each outcome (test meals vs. control), Tukey's post hoc test will be applied.

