5.2 Analysis methods

The primary endpoint, AUC of either lycopene or beta carotene will be analysed using a linear mixed model using randomization sequence and treatment (test meal) as fixed terms and patient within sequence as a random term taking into account the cross-over design as described in chapter 5 of "Cross-Over Trials", Senn (2002). Baseline will be included as a co-variate.

Assumptions of normality and equality of variance will be verified by normality plots and boxplots, respectively. If data is non- normally distributed, log transformation will be attempted.

Non-parametrical analysis (Friedman tests followed by Wilcoxon- Mann- Whitney test) may be chosen in case data is not normally distributed, if log-transformation is not successful, though based on earlier studies data normally follows normal distribution.

The secondary endpoints - triglycerides, and if feasible additional carotenoids (see 5.1 above) will be analysed by the same methodology.

A linear mixed model will be first performed for each main outcome, with either baseline corrected AUC of lycopene or beta-carotene as the observed, dependent variable, and randomization sequence, test-meal as the independent variable (fixed factor) and patient within sequence as random factor. Pairwise comparisons of the intervention will be performed by means of Tukey's post-hoc test. Additionally, sensitivity analysis with the original outcomes (lycopene or beta-carotene) as dependent, randomization sequence, test meal and baseline concentration of the outcome as fixed factors and patient within sequence as random factor. 95% confidence intervals will be reported for the main outcomes.

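### SAP 5.2's optional rank fallback follows Friedman with the Wilcoxon-Mann-Whitney test, an independent-samples test, although every meal contrast is within the same men

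*SAP*

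**What the plan says.** SAP 5.2 analyses each primary AUC with a linear mixed model that has a random patient term, followed by Tukey comparisons. If the data are not normal, a log-transformation is tried. After that comes a rank route, "Friedman tests followed by Wilcoxon- Mann- Whitney test", which "may be chosen in case data is not normally distributed, if log-transformation is not successful". The same section adds that earlier studies lead the authors to expect normal data.

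The design is within-subject throughout:
- SAP 2.4: "Patients meeting the inclusion criteria will receive three different interventions".
- SAP 2.7 lists three meal-against-meal contrasts for each carotenoid, beginning with "Protein containing meal 1 vs. control meal".
- SAP 2.6: "a 6x3 Williams Crossover inequality test of paired differences will have 96% power", and "each pairwise test is at the two-sided 0.83% significance level".

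SAP 3.1 instead splits 0.05 over the two carotenoids (0.025 each) and uses Tukey within each.

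Protocol 11 has a different fallback: "Non parametrical analysis (Friedman tests followed by individual t-tests) may be chosen in case data is not normally distributed". It also states that no log-transformation will be done. Neither document names the Wilcoxon signed-rank test.

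**The concern.** Friedman ranks the three meals within each man and so keeps the pairing. The named follow-up pools the values of two meals and ranks them as if they came from two separate groups, so differences between men return to the comparison as noise. A cross-over is run to remove that noise, and the SAP's power figure assumes that it has been removed.

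At stake is power for the individual meal contrasts if the fallback is used. With positively correlated pairs, Mann-Whitney overstates the variability of the meal difference. It then rejects too seldom, both when there is no effect and when there is one.

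**Working it through.** **1. The plan's own figure.** Inputs from SAP 2.6: difference 4, SD of paired differences 4, two-sided alpha 0.05/6 = 0.00833, and 4 men in each of 6 sequences. (SAP 2.6 prints this quotient as 0.083; the 0.83% beside it is correct and is used here.) Paired noncentral t, with noncentrality (difference/SD) × √N and df = 6 × (n per sequence − 1):
- N=24: noncentrality 1 × √24 = 4.90, df 18, power 96.2% (SAP: 96%).
- N=18: noncentrality 1 × √18 = 4.24, df 12, power 83.5% (SAP: 83%).

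Both stated figures reproduce as a paired calculation.

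**2. What dropping the pairing does.** Let ρ be the within-subject correlation between two meals and σ the per-meal SD. The mean paired difference has variance 2σ²(1−ρ)/N, whereas an independent-samples comparison treats it as 2σ²/N. Holding the SD of paired differences at 4 gives σ = 4/√(2(1−ρ)):
- ρ = 0: 4/√2 = 2.83
- ρ = 0.3: 4/√1.4 = 3.38
- ρ = 0.5: 4/√1 = 4.00
- ρ = 0.7: 4/√0.6 = 5.16

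The shift of 4 stays the same while the spread that Mann-Whitney sees grows. The paired test sees the same differences at every ρ.

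**3. Simulated power.** Both tests were applied to the same simulated pairs at two-sided 0.83%, with no Friedman gate and 20,000 to 40,000 trials per cell in the full rows. The documents give neither ρ nor a distribution, so both are assumed. Exponential means that subject effects and errors are both centred exponential. Lognormal means normal subject effects with lognormal errors. Gamma means shape 4 for both.

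| N | Model | Mann-Whitney power (%) at ρ = 0 / 0.3 / 0.5 / 0.7 | Signed-rank power (%) |
|---|---|---|---|
| 24 | Normal | 97.2 / 91.3 / 77.2 / 42.1 | 95.4–95.7 |
| 24 | Exponential | 99.3 / 96.9 / 90.5 / 69.5 | 96.6–96.8 |
| 24 | Lognormal | 99.8 / 98.6 / 90.3 / 50.7 | 97.3–97.6 |
| 24 | Gamma (ρ 0.3 and 0.5 only) | – / 93.5 / 82.1 / – | 96.1–96.2 |
| 18 | Normal | 89.5 / 75.5 / 54.6 / 21.9 | 81.6–82.5 |
| 18 | Exponential | 95.7 / 87.5 / 73.9 / 46.1 | 87.1–87.7 |
| 18 | Lognormal | 98.4 / 92.0 / 71.9 / 27.7 | 88.4–89.0 |

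N=18 is the SAP's case of one drop-out per sequence. At ρ = 0.5 with normal data the loss is 95.4 − 77.2 = 18 points at N=24 and 81.6 − 54.6 = 27 points at N=18.

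**4. Direction of the error.** With no meal difference (exponential, N=24, nominal 0.83%), Mann-Whitney rejects in 0.75 / 0.14 / 0.03 / below 0.01% of trials at ρ = 0 / 0.3 / 0.5 / 0.7. The test is conservative.

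**5. Sensitivity to level and gate.** Exponential, N=24, Friedman gate at 0.025, then 0.025 per pair, third meal equal to control: Mann-Whitney 99.7 / 99.0 / 96.9 / 87.4% against 98.9–99.0% for signed-rank. The loss is smaller at this looser level. A gate also lowers the paired test: with normal data, third meal midway, gate 0.025 and 0.83% per pair, signed-rank power is about 91%.

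**The case against.** **Reach is small.** The route is permitted rather than required, it needs two failures in turn, and the SAP expects normal data. This stands and keeps the point minor. The route can still be reached. A baseline-corrected AUC at or below zero has no logarithm, and SAP 5.2 applies the same methodology to triglycerides and additional carotenoids.

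**It is probably a naming slip.** Putting Friedman first suggests that the paired Wilcoxon test was meant. That is plausible, but nothing elsewhere in either document corrects it, and an analyst who follows the text would run the independent-samples test. The Protocol does not settle it. Its follow-up is t-tests, and its remark that each subject is compared with himself suggests paired ones, which still differ from the SAP's test.

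**Little is lost at low correlation.** This is partly true, but it depends on the shape of the data. At ρ = 0.3 and N=24 the exponential model shows no loss (96.9 against 96.6–96.8%), while the gamma model shows 93.5 against 96.1% and the normal model 91.3 against 95.4–95.7%. No general threshold for when the loss begins can be given.

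**Stronger readings that the documents do not support.** A reader might infer that the wrong test inflates false positives; under positive correlation it does the opposite. A reader might also infer that the primary analysis or the 96% power is undermined. It is not: the mixed model has a random patient term, and the 96% is a paired figure that reproduces.

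**Conclusion.** The point holds and is minor. The follow-up test named in SAP 5.2 does not fit a within-subject design. The consequence is confined to an optional fallback and is a loss of power only. At the SAP's planning values, N=24, two-sided 0.83% and no Friedman gate, Mann-Whitney power is about 91% or more at correlation 0 to 0.3, 77 to 91% at 0.5 and 42 to 70% at 0.7. Signed-rank power is about 95 to 98%. The loss is larger at N=18 and smaller if a looser per-test level is used. The conclusion that the test is wrong rests on the design alone. The size of the loss rests on the assumed correlations and distributions, which the documents do not supply.

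**What to change.** In SAP 5.2, replace the Wilcoxon-Mann-Whitney test with Wilcoxon signed-rank tests on the within-subject differences between meals. For each contrast, use all men who have both meals. This needs stating because SAP 3.2 and 4.3 keep men with two of three visits, whereas Friedman needs all three.

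Test each contrast at a Bonferroni level of 0.83%. Tukey in SAP 3.1 does not carry over to rank tests, so a level has to be named. The two SAP sections lead to the same one here: 0.05/6 = 0.00833 from SAP 2.6, and 0.025/3 = 0.00833 from the 0.025 per carotenoid in SAP 3.1. Their disagreement over the mixed-model contrasts is a separate matter.

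Reconcile Protocol 11 with SAP 5.2 so that both name the same paired fallback and the same log-transformation policy.

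The cost is wording in two documents, best settled before the data are analysed. The primary endpoint, mixed model, sample size and data collection do not change. The paired test will not give 96% power in every setting, because a Friedman gate lowers power for either follow-up test.

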5.3 Missing data

Individual time-points, if missing, during the clinical days will be estimated by using multiple imputations (Multivariate Imputation by Chained Equations).

For complete missing data-sets (1 or 2 clinical days missing), see withdrawal/follow-up.

5.4 Harms

Severe adverse effects will be noted, and inclusion of data in the final dataset will be discussed between the PI, the CIEC team and the statistician based on a case-by-case scenario. The identity of the subject will be kept confidential and not shared by the CIEC.

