Selected candidates will undergo an informed consent process during which they will be educated individually about the goals, procedures and possible risks of the study. The participant will receive a copy of both the “Informed Consent” and the “Participants Information’s sheet”. Also a list of foods to be avoided during the washout-out period, together with a second list of alternative foods will be given to each participant (see attachment). The participant may sign the consent form at the initial evaluation, or he/she may take a copy home for further consideration and sign it at a later visit to enroll in the study.

Experimental Design

This is a human proof-of concept, post-prandial randomized cross over study. Twenty four, free-living human participants (age 20-50 years, male) will be recruited. A placebo-control is not possible in sight of the amount protein that will be consumed, and the lack of a surely negative control that could be given instead of proteins and that would not be distinguishable from proteins in terms of color, taste and texture.

All participants will be instructed to avoid foods rich in carotenoids before clinical visits. On clinical visit days, participants will be asked to report at the CIEC’s facilities, starting from 7:30 am, and a baseline blood sample (20 ml) will be drawn at 0h time point. A trained nurse will insert a cannula in the forearm of the participant that will be left in place during the whole staying for the commodity of the participant.

Immediately after the baseline blood draw, a test meal composed of a mixture of carrot and tomato juice (350 mL in total), to which 5 mL of peanut oil will be added, 40 g of toasted bread (white wheat, with 10 g margarine plus 20 g cream-cheese) and a glass of water (approx. 300 mL) which may or may not contain 30 g of proteins (either a plant-

[figure not shown]
based protein or a dairy-based proteins) will be served. The entire test meal must be eaten within 30 min, under supervision.

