The first washout week starts on day 1 after the preliminary visit and will have a duration of 14 days during which the participants will be asked to stay on a low carotenoid diet (i.e. to avoid the intake of colored fruits and vegetables), to reduce the basal levels of blood circulating carotenoids. This first appointment will be followed by a 1 week washout period, during which he/she will continue on a low carotenoid diet (3rd week of washout diet). At the end of the 3rd week of washout, the second appointment at the CIEC will take place. The procedure for this day is the same as mentioned above. The second appointment is followed by the 4th and last washout week and at the end the participant will have the 3rd and last appointment at CIEC, which will be identical to the other visits. For all washout periods the participants will be asked to fill a provided food journal, on a daily basis, where they will write down what they have eaten during the day. This will be used to check compliance with the washout period and better interpret personal data.

Please find in Figure 3 a scheme of the participant’s schedule during the trial phase.

[figure not shown]

Figure 3 – Representative scheme of the participants’ schedule during the trial phase.

Data management:

The data collected in this study (lifestyle questionnaires, urine and blood samples, carotenoid plasma and plasma-TRL fraction analysis -a special fraction isolated from blood plasma-, biometric measures) will be used to investigate the influence of dietary proteins on the bioavailability, that means uptake and usage of carotenoids by the human body. The results of the investigation will possibly be published in international scientific journals without detriment to the subject's privacy.

The data collected will be treated in a strictly confidential manner and will be kept up to five years after completion of the study. The processing of the data will be done by means of a code (pseudonimisation). This code does not identify participants and will only be used for the scientific treatment of the results.

According to the provisions of the amended Grand-Ducal Law of 2nd August 2002 on the protection of individuals with regard to the processing of personal data, a notification will also be submitted to the 'Commission Nationale pour la Protection des Données' (CNPD).

Insurance:

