13. RISKS AND POSSIBLE INCONVENIENTS OF THE STUDY

Risk for subjects:

The risks associated with this study protocol in the population described above are minimal. No invasive procedures will be used in this study apart from peripheral blood drawings. There are minor risks associated with venipuncture such as mild discomfort, fainting or bruising. Less commonly, a small clot, swelling of the vein, infection, or bleeding may occur at the site of puncture. All venipuncture procedures and blood samplings will be performed by a trained nurse from the CIEC.

Participants will be asked in advance for any kind of food allergies or intolerances (e.g. gluten or milk) that are not compatible with the test meals and midday and evening snacks, given throughout the days of the trial. Any participant

showing new medical problems that are not easily explained (e.g. colds) or that requires the use of medication (e.g. antibiotics) will be withdrawn from the study.

Indeed, allergies against various proteins, including those that can be selected, have been reported. For soy protein isolate, two proteins β -conglycinin and glycinin have been suggested to be the major fractions containing allergens [32, 33], affecting approximately 0.4% of children, making soy allergy about half as common as peanut allergy [34]. The latter allergy is caused by eleven allergenic proteins [35] and Ara H2 protein is the most potent allergen [36]. However, in refined peanut oil, this protein is not expected to be present [37]. For whey protein isolate, α -lactalbumin and β -lactoglobulin have been stated as the main allergens, affecting up to 1–3% of adults and 3–8% of infants [38] [39]. When α S1-casein seems to be a major allergen of sodium caseinate according to IgE and T cell recognition data [40], and affecting about 5-6% of young children [41], α 2 chain has been reported as a main allergen of gelatin bovine, and affecting 3% of children with a history of beef meat allergy [42]. We will carefully question the participants regarding any allergies that they may have encountered and exclude any subject with a history of allergic reactions toward peanut, soy, or milk protein.

Carotenoids in amounts similar as consumed in our study are consumed within daily diets and have been served, also within fruits and vegetables in previously in other human studies (Unlu et al. 2005; Bohn et al. 2011, Borel et al, 2017) with no observed adverse effects.

Drop-outs and power calculation:

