3.2 Adherence and protocol deviations

The adherence to the intervention will be assessed based on the combined entry in the participant's study log-book, which each participant will fill out. Deviations will be discussed between the PI, CIEC and statistician and decisions for removal of subjects and collected data from the study be discussed on a case-by-case scenario. Deviations will be :

- a) Not fasting at least 10 h overnight
- b) Eating something in the morning before any of the test-meals served at the LIH.
- c) Not consuming the entire test meal within a maximum of 30 minutes.
- d) Not conducting any washout before the study.
- e) Dropping out after the first clinical day

When subjects have completed successfully at least 2 clinical visits (any 2 out of 3), their data will be analysed, if the permission from the subject is granted.

Minor deviations from the protocol that will therefore be tolerated (not dropping out):

- Drinking water during the overnight fasting
- Eating carotenoid containing foods during the washout-period, as long as the individual food items in question are listed in the volunteer's booklet
- Up to 2 missing time-points (any 2 out of 8) during the clinical days.

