4.3 Withdrawal/ follow-up

Participants are free to withdraw from the study at any moment if they desire to do so. However, we will try our best in terms of follow-up to keep subjects in the study. Any participant showing new medical problems that are not easily explained (e.g. colds) or that requires the use of medication (e.g. antibiotics) will be withdrawn from the study.

Subjects that have at least completed 2 clinical days will be kept for statistical analysis, and given that subjects agree to keeping their data. Otherwise, the cases will be removed from analysis.

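### The SAP records only severe adverse effects, and no rule says how a visit is handled when a fully eaten test meal is vomited

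*SAP*

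**What the plan says.** **Recording of harms.** SAP 5.4 reads: "Severe adverse effects will be noted, and inclusion of data in the final dataset will be discussed". It gives no severity scale, collection method, collection window or summary table. The Protocol text contains no procedure for recording adverse events.

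**Expected harms.** Protocol 13 describes mainly mild procedural risks: "There are minor risks associated with venipuncture such as mild discomfort, fainting or bruising". It adds: "Less commonly, a small clot, swelling of the vein, infection, or bleeding may occur at the site of puncture". It also discusses food-protein allergy.

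**Withdrawal.** Protocol 13 and SAP 4.3 have a separate rule: "Any participant showing new medical problems that are not easily explained (e.g. colds) or that requires the use of medication" is to be withdrawn. That rule does not ask for the event to be recorded.

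**Deviations.** Of deviations (a) to (e) in SAP 3.2, the one about intake of the test meal is "Not consuming the entire test meal within a maximum of 30 minutes". For deviations, SAP 3.2 has "decisions for removal of subjects and collected data from the study be discussed on a case-by-case scenario".

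**Analysis sets.** SAP 2.1 and 3.3 exclude participants with major deviations from the per-protocol set. Neither section defines a major deviation. SAP 3.3 makes intention to treat the standard.

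**The concern.** Two gaps follow from the wording of SAP 5.4.

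The first concerns reporting. If only severe effects are noted, a report of few or no harms could reflect the rule rather than what happened, and tolerability could not be compared between meals.

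The second concerns the primary endpoint. The AUC in the TRL fraction stands for newly absorbed carotenoid, and a meal lost by vomiting cannot be fully absorbed. The meals differ by 30 g of protein in the drink, so tolerability could differ by meal. A loss tied to one meal would then look like an effect of that protein on bioavailability. Without a record, no sensitivity analysis could separate the two.

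**Working it through.** **1. Does any rule catch a non-severe vomiting episode after a complete meal?**

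| Rule | Triggered? |
|---|---|
| SAP 5.4, severe effects | No, if judged not severe |
| SAP 3.2 (a), (b), (d), (e): fasting, eating beforehand, washout, drop-out | No |
| SAP 3.2 (c), whole meal within 30 minutes | No, the meal was eaten |
| SAP 4.3 and Protocol 13, withdrawal | Only if unexplained or medication is needed; no recording required |
| SAP 2.1 and 3.3, major deviation | Undefined, so open to judgement |

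Nothing requires a record or starts a review. SAP 2.2 also keeps negative areas in the AUC, so an unusually low value would not be removed on its size alone.

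**2. Who would decide on an unscripted exclusion?** SAP 2.4 calls the trial double blinded. Protocol 10 (Experimental Design) says that no control is available that would match protein in colour, taste and texture. The people deciding may therefore know the meal.

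**3. Reproducing the plan's power.** Inputs from SAP 2.6: N = 24, difference 4 (20 vs 24), SD of paired differences 4, two-sided alpha 0.05/6 = 0.00833. I used a noncentral t with df = N − 6 and noncentrality (4/4) × √N.

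- N = 24: √24 = 4.90, power 96.2% (stated 96%).
- N = 18: √18 = 4.24, power 83.5% (stated 83%).

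**4. Illustration: one vomited protein-meal visit is kept.** The fraction f of the AUC that remains is my assumption; the documents give none. That participant's paired difference shifts by s = (1 − f) × 24. The expected mean difference becomes 4 − s/24. The expected sample variance becomes 16 + s²/24, because one shifted value among n adds s²/n. Power comes from simulation (40,000 trials, df = 18).

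| f | s | Mean difference | Variance | SD | Power |
|---|---|---|---|---|---|
| No event | 0 | 4.0 | 16 | 4.0 | 96% |
| 0.50 | 12 | 3.5 | 16 + 6 = 22 | 4.7 | 78% |
| 0.25 | 18 | 3.25 | 16 + 13.5 = 29.5 | 5.4 | 50% |
| 0 | 24 | 3.0 | 16 + 24 = 40 | 6.3 | 20% |

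Much of the loss comes from the larger variance. With df = N − 1 the three powers are 80%, 53% and 23%.

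**5. The same visit is excluded.** With n = 23 pairs and df = 17, power is 95.0%.

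Steps 4 and 5 use a paired comparison of one protein meal with control, not the full mixed model. They also take a protein-meal loss against a true benefit. A vomited control meal would move the mean difference the other way.

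**The case against.** **The per-protocol set might exclude the visit anyway.** A reader might infer that the plan keeps a vomited-meal visit in the per-protocol AUC as a valid value. It does not say so. The set is for those who strictly followed the protocol, major deviation is undefined, and an episode judged severe goes to case-by-case review. Participants are on site for about 10.5 hours, so vomiting there would be hard to miss. This objection stands against the strong reading. It does not supply a rule, and being noticed is not the same as being recorded.

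**SAP 5.4 is not the only text on harms.** The withdrawal rule would catch, for example, an infection needing antibiotics, and a severe allergic reaction would be noted under SAP 5.4. Both stand, but neither leads to non-severe events being recorded.

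**Late harms after the last visit.** Protocol 10 says of the cannula: "A trained nurse will insert a cannula in the forearm of the participant that will be left in place during the whole staying". It says of the schedule: "at the end the participant will have the 3rd and last appointment at CIEC". A reader might infer that the collection window is too short for late complications. The documents do not support that. They state no window, give no onset times for the procedural risks, and call visit 3 the last appointment, not the last contact. Stool participants return samples afterwards (up to 6 in the Protocol; SAP 2.3 has two for complete collection and six for an aliquot). At most, the window is unspecified.

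**Low risk.** Protocol 13 calls the risks minimal and reports no adverse effects at similar carotenoid intakes. That lowers the urgency, but the statement about intakes does not address 30 g of added protein.

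**Missing text.** Some pages were not available, and the Protocol's numbering passes from 13 to 15. The finding is limited to the text supplied.

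**Conclusion.** The point holds in a limited form. No rule in the text supplied requires non-severe adverse effects to be recorded, and none says how to treat a visit when a fully eaten test meal is vomited. Any exclusion would be unscripted and possibly made with knowledge of the meal.

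The size is conditional. If one of 24 protein-meal visits is affected and keeps 0% to 50% of its AUC, the expected difference falls by 0.5 to 1.0 of the 4-point target, and power falls from 96% to about 20% to 78%. Excluding that pair leaves about 95%. Both the event and the residual AUC are assumptions, so these figures show sensitivity, not an expected loss. The documents do not support a claim that such events are likely or that the result will be biased.

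Label: cheap improvement.

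**What to change.** 1. **SAP 5.4:** replace severe adverse effects with adverse events of any severity, recorded with onset time and test meal and tabulated by meal.
2. **Visit sheet:** add a yes/no and time entry for vomiting, and another for diarrhoea, over 0 to 10 h.
3. **SAP 3.2:** add vomiting after the test meal within the sampling period as a deviation that removes that visit, not the participant, from the per-protocol set. This fits the existing rule that two completed visits out of three are enough.
4. **SAP 2.1 and 3.3:** align the per-protocol wording, which now excludes whole participants, with visit-level removal.
5. **Analyses:** leave ITT unchanged and report per-protocol as a sensitivity analysis.

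Diarrhoea should be recorded but should not exclude a visit. It may be an effect of the meal, and Protocol 7 names gastro-intestinal passage time as a possible influence on absorption, so dropping those visits could itself bias the comparison. A short contact after visit 3 is optional.

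**Cost and limit:** the cost is one visit-sheet line, one table, and possibly a few visits lost from the per-protocol set. The change makes that set informative about lost meals. It does not remove any such bias from the ITT result.
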